14.3.5 Displays of Laboratory Results

14.3.5.1 Chemistry Results

Table 57: Summary of ALT Results Values and Change from Baseline by Study Days — Safety Population

Study Day	Treatment Group	Value at Visit						Change from Baseline					
		n	Mean	SD	Median	Min	Max	n	Mean	SD	Median	Min	Max
Day 1	Treatment A (N=X)	x	x.x	x.xx	x.x	x.x	x.x	-	-	-	-	-	-
	Treatment B (N=X)	x	x.x	x.xx	x.x	x.x	x.x	-	-	-	-	-	-
Repeat Rows for Study Days 3, 5, 8, 11, 15, and 29		x	x.xx	x.xx	x.xx	x.x	x.x	x	x.x	x.xx	x.x	x.x	x.x
		x	x.xx	x.xx	x.xx	x.x	x.x	x	x.x	x.xx	x.x	x.x	x.x

SD= Standard Deviation. Min- Minimum. Max= Maximum. N=Number of subjects in the Safety population.

Tables with similar format:

Table 58: Summary of AST Results Values and Change from Baseline by Study Days — Safety Population

Table 59: Summary of Bilirubin Results Values and Change from Baseline by Study Days — Safety Population

Table 60: Summary of Creatinine Values and Change from Baseline by Study Days — Safety Population

Table 61: Summary of eGFR Results Values and Change from Baseline by Study Days — Safety Population

[Implementation note: Add footnote that eGFR values reported as >60 are analyzed as 61 and those reported as >90 are analyzed as 91.]

Table 62: ALT Results by Baseline Ordinal Score, Severity and Study Days — Safety Population

Study Day	Baseline Ordinal Score	N	Severity ^a						
			None-Grade 2		Grade 3		Life Threatening/ Grade 4		Missing
			n	%	n	%	n	%	n
Baseline									
Treatment A	5	x	x	x.X	x	x.X	x	x.X	x
	6								
	7	x	x	x.X	x	x.X	x	x.X	x
	Any BOS	x	x	x.X	x	x.X	x	x.X	x
Treatment B	5	x	x	x.X	x	x.X	x	x.X	x
	6								
	7	x	x	x.X	x	x.X	x	x.X	x
	Any BOS	x	x	x.X	x	x.X	x	x.X	x
Repeat Rows or Study Days 3, 5, 8, 11, 15, 29									
Maximum Severity Post Baseline									
Treatment A	5	x	x	x.X	x	x.X	x	x.X	x
	6								
	7	x	x	x.X	x	x.X	x	x.X	x
	Any BOS	x	x	x.X	x	x.X	x	x.X	x
Treatment B	5	x	x	x.X	x	x.X	x	x.X	x
	6								
	7	x	x	x.X	x	x.X	x	x.X	x
	Any BOS	x	x	x.X	x	x.X	x	x.X	x
N=Number of subjects in the Safety population with a non-missing lab value at the respective time point. n= Number of unique subjects that satisfies the row criteria and have the corresponding lab severity. The "Maximum Severity Post Baseline" rows indicate the maximum severity experienced by each subject at any time point post baseline, including unscheduled assessments.									
^a Severity as per NIAID Division of AIDS (DAIDS) Table for Grading the Severity of Adult and Pediatric Adverse Events, Corrected Version 2.1 (July 2017).									

Tables with similar format:

Table 63: AST Results by Baseline Ordinal Score, Severity and Study Days — Safety Population

Table 64: Bilirubin Results by Baseline Ordinal Score, Severity and Study Days — Safety Population

Table 65: Creatinine Results by Baseline Ordinal Score, Severity and Study Days — Safety Population

Table 66: eGFR Results by Baseline Ordinal Score, Severity and Study Days — Safety Population

[Implementation note: Add footnote that eGFR values reported as >60 are analyzed as 61 and those reported as >90 are analyzed as 91.]

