2.3.2 Potential Risks of Remdesivir

Remdesivir is an FDA approved antiviral and may be obtained as part of standard care outside the clinical trial. For the purpose of the BET-A study, remdesivir is still considered a study product being used as part of an investigational trial and it will be tracked and monitored accordingly.

Transaminase elevations have been observed in healthy volunteers who received remdesivir; the transaminase elevations were mild (Grade 1) to moderate (Grade 2) in severity and resolved upon discontinuation of remdesivir. Transaminase elevations have also been reported in patients with COVID-19 who received remdesivir.

In ACTT-1, the collection of adverse event (AE) data in this trial was limited to severe (Grade 3) or potentially life-threatening (Grade 4) AEs, serious adverse events (SAEs), AEs leading to study drug discontinuation, and moderate (Grade 2) severity or higher hypersensitivity reactions. Rates of adverse reactions (\geq Grade 3), serious adverse reactions, and adverse reactions leading to treatment discontinuation are presented in Table 2.

 Table 2. Summary of Adverse Reaction Rates in Subjects with Mild, Moderate, or Severe COVID-19 in ACTT-1

Types of Adverse Reactions	Remdesivir N=532 n (%)	Placebo N=516 n (%)
Adverse reactions, Grades ≥ 3	41 (8%)	46 (9%)
Serious adverse reactions	2 (0.4%) ^a	3 (0.6%)
Adverse reactions leading to	11 (2%) ^b	15 (3%)
treatment discontinuation		

a Seizure (n=1), infusion-related reaction (n=1).

b. Seizure (n=1), infusion-related reaction (n=1), transaminases increased (n=3), ALT increased and AST increased (n=1), GFR decreased (n=2), acute kidney injury (n=3).

There is the potential of the SARS-CoV-2 developing resistance to remdesivir, which could result in decreased efficacy. The clinical impact of the development of resistance is not clear at this time.

Coadministration of remdesivir and chloroquine phosphate or hydroxychloroquine sulfate is not recommended based on cell culture data demonstrating an antagonistic effect of chloroquine on the intracellular metabolic activation and antiviral activity of remdesivir.

See Package Insert for full discussion of clinical experience and risks.

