- Blood for screening laboratory evaluations, if not done as part of routine clinical care in the preceding 48 hours, should be collected to evaluate the following parameters:

- ALT
- AST
- Serum creatinine (and calculate eGFR)
 - Any automated calculation by the clinical laboratory or published formula for this calculation is acceptable. The site should select a formula to be used for all subjects enrolled at the site for the duration of the study.
- Urine or serum pregnancy test (in women of childbearing potential).

Clinical screening laboratory evaluations will be performed locally by the site laboratory. A screening lab (i.e., from the hematology and chemistry laboratory panels) may be repeated once if, in the opinion of the investigator, the laboratory abnormality is due to an intercurrent transient condition or it is an aberrant laboratory value. The overall eligibility of the subject to participate in the study will be assessed once all screening values are available. If performed just prior to randomization, data obtained from screening can also be a baseline assessment of severity and efficacy.

Study subjects who qualify will be randomized in the interactive response technology (IRT) system, and all others will be registered as screen failures only in the EDC system. The ordinal scale should be done at the time of randomization; the site will need this data to randomize the subject. The study team has 24 hours to complete other Day 1 baseline assessments prior to the first study product administration including the collection of the OP swab and blood, assessment of the ordinal scale and NEWS, and completing or recording a baseline physical examination that was done. Clinical laboratory tests performed as part of routine clinical care in the 48 hours prior to enrollment will be accepted for determination of eligibility.

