9.6. Clinical Laboratory Evaluations

Clinical safety laboratory AEs are collected Study Days 1, 3, 5, 8, and 11 (while hospitalized); and outpatient Study Days 15 and 29 (if attends in-person visit or still hospitalized). Parameters evaluated include WBC, differential, Hgb, PLT, creatinine, (and calculate an estimated glomerular filtration rate (eGFR); the formula used is determined by the sites, but should be consistent throughout the study), total bilirubin, AST, ALT, and INR. Additional laboratory parameters may be summarized based on each intervention's safety profile. Laboratory safety parameters will be graded according to the NIAID Division of AIDS (DAIDS) Table for Grading the Severity of Adult and Pediatric Adverse Events, Corrected Version 2.1 (July 2017).

The distribution of Grade 3 and 4 chemistry and hematology laboratory results by maximum severity, time point, ordinal score and treatment group will be presented in [Table 62](#) through [Table 66](#) for chemistry and [Table 76](#) through [Table 81](#) for hematology. Absolute values and change from baseline of laboratory values will be summarized by mean, SD, median, minimum, and maximum results at Study Days 1, 3, 5, 8, 11, 15 and 29 in [Table 57](#), through [Table 61](#) for chemistry and [Table 67](#) through [Table 75](#) for hematology. Individual laboratory results are provided in [Listing 27](#) for chemistry and hematology and [Listing 29](#) for urine pregnancy results.

Markers of inflammation and coagulation results for CRP, ferritin, d-dimer, LDH, and fibrinogen will be summarized by mean, SD, median, minimum, and maximum results at Study Day 1 and Study Visit (not necessarily actual) Study Days 3, 5, 8, 11, 15 and 29 by treatment as well as change from baseline at each post-Study Day 1 visit ([Table 82](#)). Figures with mean and SD over time will also be presented by treatment ([Figure 31](#), [Figure 32](#), [Figure 33](#), [Figure 34](#), [Figure 35](#)). Individual results for markers of inflammation are presented in [Listing 28](#).

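### Table 61 treats eGFR values reported only as above 60 or above 90 as exactly 61 and 91, which pulls the mean change from baseline toward zero

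*SAP*

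**What the plan says.** SAP Sections 3.1.2.2, 3.2 and 4.5 list eGFR over time among the safety objectives, endpoints and variables. Section 9.6 sets the summary for seven scheduled days, the first being Day 1 and the last Day 29: "Absolute values and change from baseline of laboratory values will be summarized by mean, SD, median, minimum, and maximum results at Study Days". For eGFR the shell is "Table 61: Summary of eGFR Results Values and Change from Baseline by Study Days — Safety Population". Its implementation note fixes the handling of ceiling values: "eGFR values reported as >60 are analyzed as 61 and those reported as >90 are analyzed as 91". The same note sits under the eGFR severity table, Table 66.

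The values come from local practice. Protocol Section 8.1.1 states: "Any automated calculation by the clinical laboratory or published formula for this calculation is acceptable". It then asks for consistency within a site only: "The site should select a formula to be used for all subjects enrolled at the site for the duration of the study". SAP Section 9.6 agrees: "the formula used is determined by the sites, but should be consistent throughout the study". Neither document sets a common reporting ceiling, requires an uncapped value, or plans a central calculation of eGFR. No count of ceiling-limited values and no censored-data method is specified.

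Creatinine is a safety laboratory test at the same visits. It is summarised in Table 60 (value and change) and graded in Table 65, with no substitution note on either.

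**The concern.** A result of >60 says only that eGFR is somewhere above 60. Replacing it with 61 puts every such subject at the lowest whole number consistent with the report, and change from baseline is then computed as if 61 had been measured. Declines that stay above the ceiling disappear, and declines that cross it are shortened. A rise from a low baseline is cut off in the same way. Because the baseline value is the one more often capped when kidney function worsens, the net effect on a true decline is attenuation.

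This matters because eGFR is a listed safety outcome and a fall in renal function is a plausible thing to look for. In Protocol Table 2, the footnote on remdesivir-arm adverse reactions leading to discontinuation in ACTT-1 lists 11 events, of which 5 are renal (2 decreased GFR, 3 acute kidney injury). All subjects here receive remdesivir, so a renal effect of the backbone would appear as within-arm change in both arms, which is the quantity the substitution shrinks.

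**Working it through.** There is no figure in the plan to reproduce. The check applies the SAP rule to true values and compares recorded with true change.

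**Rule.** For a reporting ceiling c (60 or 90): recorded = c + 1 if true value > c; otherwise recorded = true value. Recorded change = recorded follow-up - recorded baseline.

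**Individual cases (the true values are assumed).**

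| Ceiling | True baseline to follow-up | True change | Recorded change |
|---|---|---|---|
| 60 | 110 to 62 | -48 | 61 - 61 = 0 |
| 60 | 120 to 61 | -59 | 61 - 61 = 0 |
| 60 | 100 to 55 | -45 | 55 - 61 = -6 |
| 60 | 120 to 45 | -75 | 45 - 61 = -16 |
| 90 | 120 to 91 | -29 | 91 - 91 = 0 |
| 90 | 120 to 65 | -55 | 65 - 91 = -26 |
| 90 | 75 to 45 | -30 | 45 - 75 = -30 (exact) |

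Three patterns follow.

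- Both values above the same ceiling: recorded change is exactly 0.
- Baseline above and follow-up at or below the ceiling: the decline is recorded but understated by true baseline minus (c + 1). For 100 to 55 at c = 60 that is 100 - 61 = 39, and 45 - 39 = 6.
- Both values at or below the ceiling: no error.

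**Visit values.** Two subjects with the same eGFR above 90 at sites with different ceilings are recorded 91 - 61 = 30 units apart. This affects the pooled mean and SD at a visit. It largely cancels in within-subject change, because the formula is to stay the same within a site.

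**Group illustration.** None of these inputs is in the documents: true baseline normal with mean 85 and SD 22, limited to 20-140; follow-up = baseline x 0.85 in one arm and x 1 in the other, plus visit noise with SD 8. Simulated between-arm difference in mean change:

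| Reporting | Difference | Loss |
|---|---|---|
| No ceiling | -12.73 | 0% |
| All sites cap at 60 | -1.83 | (12.73 - 1.83)/12.73 = 86% |
| All sites cap at 90 | -8.09 | (12.73 - 8.09)/12.73 = 36% |

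In the arm with the fall, 72% of subjects are above 60 at both visits and would show exactly zero change under a 60 ceiling. With a baseline mean of 75 or 95 instead of 85, the loss under a universal 60 ceiling is about 75% or 93%.

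**Share of capped sites.** This drives the answer and is unknown. Let a be the share of subjects at sites capping at 60 and b the share at sites capping at 90, with the rest uncapped. Then

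difference = (1 - a - b)(-12.73) + a(-1.83) + b(-8.09).

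| a | b | Difference | Loss |
|---|---|---|---|
| 0 | 0 | -12.73 | 0% |
| 0.10 | 0 | -11.64 | 9% |
| 0.25 | 0 | -10.0 | 21% |
| 0.50 | 0 | -7.28 | 43% |
| 0.10 | 0.10 | -11.18 | 12% |
| 0.20 | 0.20 | -9.62 | 24% |
| 1 | 0 | -1.83 | 86% |

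In every row with capping, the movement is toward zero.

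**The case against.** The best reply is that little depends on Table 61. It is descriptive, with no test and no decision rule on eGFR. The note requires a footnote, so the substitution is disclosed, and similar conventions are used for eosinophils, D-dimer and CRP. Creatinine value, change and grade are tabulated with no ceiling, Grade 3 and 4 adverse events are collected through Day 60, and individual results are listed. The Protocol's own renal laboratory endpoint is creatinine; eGFR is added by the SAP. The risankizumab risks in Protocol Section 2.3.3 include no renal one, so a fall confined to one arm is only an illustration. Randomization is stratified by site, so reporting formats should be roughly balanced between arms.

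Most of this stands, and it limits the point to a correction of one descriptive table. A reader might infer that large renal declines in general will be recorded as no change. That is too broad: a zero needs both values above the same ceiling, and the fall from 100 to 55 is recorded, though shrunk. A reader might also infer that the trial could report no renal signal unchallenged; Tables 60 and 65 stand against that.

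Two parts do not answer the point. Disclosure in a footnote does not make the mean, SD and change statistics correct. Balance across arms does not help either: equal capping in both arms still attenuates the change within each arm and any difference between them.

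**Conclusion.** The concern holds for Table 61. Ceiling-reported eGFR values are analysed as exact numbers, so declines above a ceiling are recorded as zero, declines through it are understated, and mean change is biased toward zero. The mechanism follows from the SAP text alone.

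The size in this trial cannot be stated. Under the assumed illustration it runs from 0% with no capped sites to about 86% if every site caps at 60. The 86% should not be read as the expected loss: the SAP note itself anticipates both ceilings, and the capped share is not given.

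A reader might extend the finding to Table 66, which carries the same note. No error is shown there. That table groups results by severity grade, the grading cut-offs are not in the documents, and no example of a changed grade can be constructed from them.

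**What to change.** In the SAP, replace the 61/91 note under Table 61 with a derived variable: eGFR calculated centrally for each sample from recorded serum creatinine, age and sex, using one named published formula for all sites. Use it for visit values and change from baseline. Use the same derived value in Table 66, for consistency between the two tables rather than because an error has been shown there. Keep locally reported eGFR in the listings and for site use.

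The inputs are already collected: creatinine is a safety laboratory test at every scheduled laboratory visit, and age and sex are demographic variables. One formula also removes between-site formula differences from the pooled summaries. The cost is one derived variable and a change of SAP wording, with no new data or procedure. The downside is that analysed values may differ slightly from those the sites saw, which a footnote can state.

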14.3.5.1 Hematology Results

Table 67: Summary of White Blood Cells Results Values and Change from Baseline by Study Days — Safety Population

Study Day	Treatment Group	Value at Visit						Change from Baseline					
		n	Mean	SD	Median	Min	Max	n	Mean	SD	Median	Min	Max
Day 1	Treatment A (N=X)	x	x.xx	x.xx	x.xx	x.x	x.x	-	-	-	-	-	-
	Treatment B (N=X)	x	x.xx	x.xx	x.xx	x.x	x.x	-	-	-	-	-	-
Repeat Rows for Study Days 3, 5, 8, 11, 15, and 29		x	x.xx	x.xx	x.xx	x.x	x.x	x	x.x	x.xx	x.x	x.x	x.x
		x	x.xx	x.xx	x.xx	x.x	x.x	x	x.x	x.xx	x.x	x.x	x.x

SD= Standard Deviation. Min- Minimum. Max= Maximum. N=Number of subjects in the Safety population.

Tables with similar format:

Table 68: Summary of Platelets Results Values and Change from Baseline by Study Days — Safety Population

Table 69: Summary of Hemoglobin Results Values and Change from Baseline by Study Days — Safety Population

Table 70: Summary of INR Results Values and Change from Baseline by Study Days — Safety Population

Table 71: Summary of Neutrophils Results Values and Change from Baseline by Study Days — Safety Population

Table 72: Summary of Eosinophils Results Values and Change from Baseline by Study Days — Safety Population

[Implementation note: Add footnote that Eosinophils values reported as <0.03 are analyzed as 0.02.]

Table 73: Summary of Basophils Results Values and Change from Baseline by Study Days — Safety Population

Table 74: Summary of Lymphocytes Results Values and Change from Baseline by Study Days — Safety Population

Table 75: Summary of Monocytes Results Values and Change from Baseline by Study Days — Safety Population

Table 76: White Blood Cell Results by Baseline Ordinal Score, Severity and Study Days — Safety Population

Study Day	Baseline Ordinal Score	N	Severity ^a						
			None-Grade 2		Grade 3		Life Threatening/ Grade 4		Missing
			n	%	n	%	n	%	n
Baseline									
Treatment A	5	x	x	x.x	x	x.x	x	x.x	x
	6								
	7	x	x	x.x	x	x.x	x	x.x	x
	Any BOS	x	x	x.x	x	x.x	x	x.x	x
Treatment B	5	x	x	x.x	x	x.x	x	x.x	x
	6								
	7	x	x	x.x	x	x.x	x	x.x	x
	Any BOS	x	x	x.x	x	x.x	x	x.x	x
Repeat Rows or Study Days 3, 5, 8, 11, 15, 29									
Maximum Severity Post Baseline									
Treatment A	5	x	x	x.x	x	x.x	x	x.x	x
	6								
	7	x	x	x.x	x	x.x	x	x.x	x
	Any BOS	x	x	x.x	x	x.x	x	x.x	x
Treatment B	5	x	x	x.x	x	x.x	x	x.x	x
	6								
	7	x	x	x.x	x	x.x	x	x.x	x
	Any BOS	x	x	x.x	x	x.x	x	x.x	x
N=Number of subjects in the Safety population. n= Number of unique subjects that satisfies the row criteria.									
^a Severity as per NIAID Division of AIDS (DAIDS) Table for Grading the Severity of Adult and Pediatric Adverse Events, Corrected Version 2.1 (July 2017).									

Tables with similar format:

Table 77: Platelets Results by Baseline Ordinal Score, Severity and Study Days — Safety Population

Table 78: Hemoglobin Results by Baseline Ordinal Score, Severity and Study Days — Safety Population

Table 79: INR Results by Baseline Ordinal Score, Severity and Study Days — Safety Population

Table 80: Neutrophils Results by Baseline Ordinal Score, Severity and Study Days — Safety Population

Table 81: Lymphocytes Results by Baseline Ordinal Score, Severity and Study Days — Safety Population

Table 82: Summary of Continuous Markers of Inflammation and Immune Response by Study Day — Safety Population

Study Day	Immune Response Measure	Treatment A (N=X)						Treatment B (N=X)					P-value ^a
		n	Mean	SD	Median	Min	Max	Mean	SD	Median	Min	Max	
Day 3	C-reactive protein	xx	x.x	x.xx	x.x	x	x	x.x	x.xx	x.x	x	x	0.xxx
	Ferritin	xx	x.x	x.xx	x.x	x	x	x.x	x.xx	x.x	x	x	0.xxx
	D-Dimer	xx	x.x	x.xx	x.x	x	x	x.x	x.xx	x.x	x	x	0.xxx
	Fibrinogen	xx	x.x	x.xx	x.x	x	x	x.x	x.xx	x.x	x	x	0.xxx
	LDH	xx	x.x	x.xx	x.x	x	x	x.x	x.xx	x.x	x	x	0.xxx
Rows should be repeated for Study Days 1, 5, 8, 11, 15, and 29													

SD= Standard Deviation. Min= Minimum. Max= Maximum. N=Number of subjects in Safety population.
 Values of D-Dimer reported as <220 were analyzed as 219 and values of CRP reported as <3.0 were analyzed as 2.9.
^a P-value of tests of two sample means.

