The study will include one Master Protocol (DMID Protocol 20-0013: ACTIV-5/Big Effect Trial) and an additional “stage” for each investigational intervention included in the study. Stage-Specific Appendices will be provided, detailing the protocol interventions and any specific exceptions to the Master Protocol. One or more interventions/stages may be started at any time. The number of interventions/stages enrolling concurrently are programmatic decisions and will be based on the number of sites and the pace of enrollment. At the time of enrollment, subjects will be randomized to a stage, and then to either the active arm of that stage or the matching placebo. There will be approximately 100 subjects in each active arm of the platform trial (though this may be modified as specified in each stage-specific appendix to accommodate special circumstances). A given site will generally have no more than 3 interventions/stages at once.

See the schedule of assessments in each stage-specific appendix for assessment details. The schedule is similar to Adaptive COVID-19 Treatment Trial (ACTT) to allow evaluation of endpoints used in the larger study. Subjects will be assessed daily while hospitalized. Once subjects are discharged from the hospital, they will have a study visit on Study Days 8, 15, 22, 29 and 60 as an outpatient. The outpatient Study Days 8, 22 and 60 visits do not have laboratory tests or collection of samples and may be conducted by phone. Days 15 and 29 visits are preferred to be in person in order to collect safety laboratory testing, stored samples, and virologic assessments. However, if infection control considerations and other restrictions limit the ability to have visits at Study Days 15 and 29 in person, they may also be conducted by phone and only clinical data will be obtained.

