Oxygenation, non-invasive ventilation/high flow oxygen, invasive mechanical ventilation/extracorporeal membrane oxygenation (ECMO) will be assessed using results of the 8-point ordinal scale. Hospitalization duration will be assessed using admittance and discharge dates. Mortality will be assessed using results from the electronic case report form (eCRF) serious adverse events (SAEs) form. That is, the number of days from Study Day 1 to the date of death.

Safety will be assessed by the following:

- Cumulative incidence of SAEs up to and including Study Day 60.
- Cumulative incidence of Grade 3 and 4 clinical and/or laboratory AEs up to and including Study Day 60.
- Discontinuation or temporary suspension of study product administration (for any reason).
- Changes in WBC count with differential, hemoglobin, platelets, creatinine, total bilirubin, ALT, AST, eGFR, and INR over time (analysis of lab values in addition to AEs noted above).

Clinical labs will be drawn on Study Days 1, 3, 5, 8, 11 while the subject is hospitalized and on Study Days 15 and 29 if the subject is able to return to the clinic or is still hospitalized.

Exploratory endpoints for post-baseline usage of key concomitant COVID-19 treatments (e.g., steroids) summarized by investigational therapeutic and control arms. The details of analyses for all virology and PK exploratory endpoints will be included in a separate analysis plan(s).

The schedule of study assessments is provided in each stage-specific appendix of the SAP.

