6. GENERAL STATISTICAL CONSIDERATIONS

6.1. General Principles

This is a proof of concept double-blind placebo controlled randomized trial testing a superiority hypothesis where interventions with a two-sided p-value $< .20$ will be declared promising and will be considered statistically significant if the final two-sided p-value is $< .05$. These data will be summarized by treatment (intervention name versus placebo) and when appropriate by baseline ordinal score. Additionally, data will be described according to the appropriate summary statistics, e.g.

- Percentages/proportions/odds ratios for categorical data. For tabular summaries of percentages/proportions, the denominator (e.g., number of subjects in the specified population) will be displayed.
- Means, standard deviation, median, and/or range for continuous data, median and confidence intervals for time-to-event data.

Confidence intervals will be generated; 95% and 80% confidence intervals will be generated for primary and key secondary outcomes. For hazard ratio and odds ratio estimates, Wald confidence intervals will be used. For confidence intervals of proportions for other efficacy and safety outcomes, Blaker confidence intervals will be used.

In general, all tables will have corresponding listings of data presented unless noted otherwise.

When calculating treatment effects (e.g., differences, hazard ratios, odds ratios) from regression modelling, placebo will be used as the reference group. Subjects on interventions will only be compared to control subjects who could potentially have been randomized to that intervention (i.e., they met eligibility criteria for the intervention and are at a site where the intervention was enrolling at the time of the subject's randomization). Analyses of newly added arm(s) will be performed comparing concurrently enrolled control subjects. For any modeling that uses covariates defined in Section 6.4, the category listed last for each variable in that section will be used as the control group for the interaction analysis and covariate-adjusted analyses.

For the time-to-event analyses, the following SAS pseudocode will be used to generate stratum-specific median time to event estimates and confidence intervals and stratum-specific Kaplan-Meier curves.

```
proc lifetest data=dataset plots=(s);
  time timevariable * censorvariable(1);
  test treatmentvariable;
run;
```

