6.3.3. Safety Population

The safety population will include all randomized subjects who received at least one dose of an investigational product other than standard of care therapies, and the population will be analyzed using actual treatment group.

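### Grade 3-4 hematology and INR tables (76-81) use a different N from the matching chemistry tables (62-66); if % = n/N, the later visit rows are diluted by untested subjects

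*SAP*

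**What the plan says.** SAP Section 9.6 describes the chemistry and hematology grade tables together, as one analysis: "The distribution of Grade 3 and 4 chemistry and hematology laboratory results by maximum severity, time point, ordinal score and treatment group will be presented". The shells in Appendix 1 share the same columns (N; n and % for None-Grade 2, Grade 3 and Grade 4; a Missing count without a %) and the same rows (baseline, each visit, maximum severity post baseline).

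The footnotes differ:

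- Table 62 (ALT; format reused for Tables 63-66): "N=Number of subjects in the Safety population with a non-missing lab value at the respective time point".
- Table 76 (white cells; format reused for Tables 77-81, covering platelets, hemoglobin, INR, neutrophils and lymphocytes): "N=Number of subjects in the Safety population. n= Number of unique subjects that satisfies the row criteria".

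Table 62 also explains the maximum-severity row, including its use of unscheduled results. Table 76 does not.

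On percentages in general, Section 6.1 says: "For tabular summaries of percentages/proportions, the denominator (e.g., number of subjects in the specified population) will be displayed". Membership of the Safety population depends on dosing, not on having a sample: "The safety population will include all randomized subjects who received at least one dose of an investigational product other than standard of care therapies".

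On collection, Section 4.5 says: "Clinical labs will be drawn on Study Days 1, 3, 5, 8, 11 while the subject is hospitalized". On Days 15 and 29, labs are drawn only from subjects still in hospital or seen in person. Section 4.1 adds: "The outpatient Study Days 8, 22 and 60 visits do not have laboratory tests or collection of samples". Phone visits on Days 15 and 29 give clinical data only. SAP Table 7 specifies no imputation for safety labs.

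**The concern.** A subject who has gone home, has died, or is followed by phone has no hematology value at that visit and cannot be counted as Grade 3 or 4. If that subject stays in the denominator, the printed percentage is the rate among those tested multiplied by the share tested. It falls as discharge proceeds, whatever the drug does to blood counts.

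Two things are at stake. Within an arm, hematology and INR percentages at later visits would be lower than, and not comparable with, the chemistry percentages in the same report. Between arms, if one arm leaves hospital sooner, its printed percentages fall further even when the rate among tested subjects is equal.

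**Working it through.** The plan gives no figure on this point, so there is none to reproduce. The check asks how large the dilution would be if % = n/N.

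**Inputs**

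- Control-arm status at Day 8, SAP Table 4: scores 1-2 (not hospitalized) 0.0 + 34.6 = 34.6%; score 8 (dead) 3.5%; scores 3-7 (in hospital) 1.2 + 10.6 + 17.1 + 8.8 + 24.2 = 61.9%.
- Treatment effect: odds ratio 2, which SAP Section 4.2 gives as an example of a large effect. Values of 1, 1.25, 1.5 and 2.5 are also tried.
- Grade 3-4 rate among tested subjects: 10%, range 5% to 20%, equal in both arms. This is an assumption; the documents give no rate.

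As a check on Table 4 as an input, the sample-size formula in SAP Section 5, with 200 subjects in total and an odds ratio of 2, gives power 0.769 (alpha 0.05) and 0.921 (alpha 0.20). SAP Table 5 has 0.765 and 0.913.

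**Formulas**

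- Share tested = P(score 7 or better) − P(score 2 or better).
- Active arm: new odds = odds ratio × control odds, at each cumulative cut.
- Printed % = rate among tested × share tested.

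**Active arm at an odds ratio of 2**

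- Score 2 or better: odds 0.346/0.654 = 0.529; doubled, 1.058; probability 1.058/2.058 = 51.4%.
- Score 7 or better: odds 0.965/0.035 = 27.57; doubled, 55.14; probability 55.14/56.14 = 98.2%, so 1.8% dead.
- Share tested: 98.2 − 51.4 = 46.8%.

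**Printed Day 8 percentage for an equal rate among those tested**

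| Odds ratio | Active share tested | 10% prints as | 5% prints as | 20% prints as | Active/control ratio |
|---|---|---|---|---|---|
| 1 (same as control) | 61.9% | 6.2% | 3.1% | 12.4% | 1.00 |
| 1.25 | 57.4% | 5.7% | 2.9% | 11.5% | 0.93 |
| 1.5 | 53.4% | 5.3% | 2.7% | 10.7% | 0.86 |
| 2 | 46.8% | 4.7% | 2.3% | 9.4% | 0.76 |
| 2.5 | 41.6% | 4.2% | 2.1% | 8.3% | 0.67 |

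The ratio does not depend on the assumed rate, only on the shares tested. At an odds ratio of 2, a rate of 10 × 61.9/46.8 = 13.2% among tested active subjects would look equal to 10% in control.

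**Other rows**

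- Baseline: nearly everyone is tested, so there is essentially no dilution.
- Maximum severity: only subjects with no post-baseline lab dilute it. Protocol Section 5.2 excludes patients expected to leave within 72 hours, so most should have a Day 3 sample. If 0-5% have none (an assumption), 10% prints as 10 × (1 − 0.05) = 9.5% up to 10%.

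With the Table 62 definition of N, 10% among tested subjects prints as 10% in both arms.

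**The case against.** **The denominator is inferred.** Nothing under Table 76 says % = n/N. Where the SAP wants the Safety population as denominator it can say so, as it does under Tables 47, 48, 52 and 53. A programmer could divide by N minus Missing instead. This stands: the dilution is conditional. But N is the only denominator displayed and Section 6.1 points to it, so the ambiguity is itself a reason to settle the footnote.

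**The information is on the page.** The shell already has a Missing count in every row, so a reader can recompute the rate among those tested. This stands too, and it makes the matter one of presentation rather than hidden bias.

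**The size depends on chosen values.** The 10% rate is assumed, the 0.76 ratio needs an odds ratio of 2, and with no treatment effect there is no between-arm distortion. The Day 8 lab window is Days 7-9 (SAP Table 2), so the share tested may be somewhat above 61.9%. All of this stands.

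**A stronger inference is tempting but unsupported.** A reader might infer that the plan would hide cytopenia or coagulation harm. The documents do not bear that out. Tables 76-81 contain no test and no between-arm contrast. Grade 3-4 clinical and laboratory adverse events are counted cumulatively through Day 60, treatment-emergent events are shown with risk differences (Table 47), and death, SAE or Grade 3-4 event is analyzed as time to event (Section 9.4). The continuous hematology tables show n at each visit. None of these uses the Table 76 footnote.

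**Conditioning on being tested has its own problem.** Those still in hospital are a group selected after randomization. If the drug speeds discharge, those who remain may be sicker, and the Table 62 denominator could then overstate toxicity in the active arm. This stands, and the table should say so.

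**Conclusion.** The two sets of tables are inconsistent on a display that Section 9.6 treats as a single analysis, and the difference changes printed safety percentages if % = n/N. On that reading, Day 8 control percentages are about 38% too low relative to the rate among tested subjects (6.2% for 10%), and the active/control ratio is 0.93, 0.86 or 0.76 at odds ratios of 1.25, 1.5 or 2. This rests on Table 4 holding in the trial, on an equal assumed rate in both arms, and on testing following hospital status exactly.

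The effect is confined to visit rows after discharges begin. It would be wrong to read it as dilution of all toxicity percentages in Tables 76-81, because the baseline and maximum-severity rows barely move. It would also be wrong to read a ratio below 1 as certain, because it arises only if discharge or death timing differs by arm. This is a minor correction to supporting safety displays.

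**What to change.** In SAP Appendix 1, for Tables 76-81:

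- Adopt the Table 62 definition of N: Safety-population subjects with a non-missing value at the time point.
- For the maximum-severity row, take N as Safety-population subjects with at least one post-baseline value, and carry over Table 62's note that unscheduled results count.
- State that % = n/N.
- Keep the existing Missing count.
- Add a note that visit percentages are conditional on still being tested, so comparisons between arms remain subject to selection.

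The cost is one footnote in six table shells. Data collection, the Safety population and the other safety analyses do not change.
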